6.9 Safety Endpoints

6.9.1 Study Drug Exposure and Compliance

Exposure to study drug will be calculated separately for each treatment period and overall.

The duration of XP-8121 exposure will summarize the total time in days while taking XP-8121 in each period and overall. The duration of exposure will be calculated as: $(\text{date of last dose of study drug} - \text{date of first dose of study drug} + 1)$.

The number of doses administered will categorize each subject by total number of XP-8121 doses received within each period and overall.

The total volume (μL) administered will be the sum of the volume (μL) of drug administered in each period and overall.

The total dose (μg) administered will be the sum of the doses (μg) of drug administered in each period and overall.

6.9.2 Adverse Events

AE verbatim terms recorded by the investigator will be coded to system organ class (SOC) and preferred term (PT) using the Medical Dictionary for Regulatory Activities (MedDRA) version 26.0.

A TEAE is defined as any adverse event which occurs on or after the first dose of study drug.

All TEAEs will be assessed by the investigator for severity and for causality. Events with missing severity will be summarized as Severe. Events with missing relationship to study treatment will be summarized as related.

TEAEs marked with a relationship to study treatment of definitely related, probably related, possibly related, or missing will be considered as related TEAEs, and TEAEs summarized by relationship will count each subject once for the maximum relationship within each SOC and PT.

TEAEs will be attributed to treatment periods by comparing the start date/time of the event to the date/time of first dose within each of the treatment periods.

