### 12.1. Adverse and Serious Adverse Events

#### 12.1.1. Definition of Adverse Events

##### 12.1.1.1. Adverse Event

An AE is the development of an undesirable medical condition or the deterioration of a pre-existing medical condition following or during exposure to a pharmaceutical product, whether or not considered casually related to the product. In clinical studies, an AE can include an undesirable medical condition occurring at any time, including baseline or washout periods, even if no study treatment has been administered.

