### **12.3. Recording Adverse Events**

Adverse events spontaneously reported by the patient/subject and/or in response to an open question from the study personnel or revealed by observation will be recorded during the study at the investigational site. Clinically significant changes in laboratory values, BP, and heart rate/pulse also need to be reported as AEs. Disease -related events will be recorded as AEs if the events occur with greater frequency, severity or duration than expected. Information about AEs will be collected from the signing of consent form and followed until resolution or maximally up to 14 days after the End of Maintenance. Serious Adverse Event information will be collected from time of consent and followed until resolution. The AE term should be reported in standard medical terminology when possible. For each AE, the Investigator will evaluate and report the onset (date and time), resolution (date and time), intensity, causality, action taken, serious outcome (if applicable), and whether or not it caused the patient to discontinue the study.

Intensity will be assessed according to the following scale:

- Mild (awareness of sign or symptom, but easily tolerated)
- Moderate (discomfort sufficient to cause interference with normal activities)
- Severe (incapacitating, with inability to perform normal activities)

It is important to distinguish between serious and severe AEs. Severity is a measure of intensity whereas seriousness is defined by the criteria above. An AE of severe intensity may not be considered serious.

Should a pregnancy occur, it must be reported within 24 hrs of the first awareness of the event and recorded on Xeris' pregnancy form. Pregnancy in itself is not regarded as an AE unless there is a suspicion that a study drug may have interfered with the effectiveness of a contraceptive medication.

The outcome of all pregnancies (spontaneous miscarriage, elective termination, normal birth, or congenital abnormality) must be followed up and documented even if the patient was discontinued from the study.

All reports of congenital abnormalities/birth defects are SAEs. Spontaneous miscarriages should also be reported and handled as SAEs. Elective abortions without complications should not be handled as AEs.

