## **12.6. Clinical Laboratory Abnormalities and Other Abnormal Assessments Reported as Adverse Events and Serious Adverse Events**

Abnormal laboratory findings (eg, serum chemistry, hematology, and urinalysis) or other abnormal assessments (eg, ECG and vital signs) per se are not reported as AEs. However, those abnormal findings that are deemed **clinically significant** by the Investigator and/or delegate or are associated with signs/symptoms must be recorded as AEs if they meet the definition of an AE (and recorded/reported as an SAE if they meet the criteria of being serious) as previously described. Clinically significant abnormal laboratory or other clinically significant abnormal findings that are detected after consent or that are present at Screening and worsen after consent are included as AEs (and SAEs if serious).

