8.3 Handling of Dropouts or Missing Data

Drop-out subjects will not be replaced.

In general, there will be no replacement of missing data points. All data recorded on the eCRF for enrolled subjects will be included in data listings that will accompany the clinical study report.

When considering AE and Concomitant Medications, partial start/end dates will be managed in a conservative fashion so that if there is any possibility that the available partial information could reasonably result in the AE being treatment-emergent or the medication being concomitant, then it will be imputed as such. Specifically:

- If the start day is missing but month and year are present:
 - o If the known month/year are the same as the month/year of the first dose of treatment, then impute to the date of the first dose of treatment;
 - o Otherwise, impute the day to 01.
- If the start day and month are both missing but the start year is present:
 - o If the known year is the same as the year of the first dose of treatment, then impute to the date of the first dose of treatment;
 - o Otherwise, impute the day and month to 01January.
- If the start date is completely missing, impute to the date of the first dose of treatment, unless the end date suggests it could have started prior to this, in which case impute to 01January of the same year as the end date.
- When imputing a start date, ensure that the new imputed date is on or prior to the end date of the AE or medication.
- If the end date is missing or partial, and the AE/medication is not ongoing, then impute the missing/partial end date as follows:
 - o If the end day is missing but month and year are present:

- If the known month/year are the same as the month/year of the first dose of treatment, then impute to the date of the first dose of treatment;
 - Otherwise, impute the day to the last day of the month.
 - If the end day and month are both missing but the end year is present:
 - If the known year is the same as the year of the first dose of treatment, then impute to the date of the first dose of treatment;
 - Otherwise, impute the day and month to 31December.
 - If the end date is completely missing, impute to the date of the first dose of treatment.
 - When imputing an end date, ensure that the new imputed date is on or after the start date of the AE or medication.

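### The SAP's treatment-emergent definition has no worsening clause, so whether a Screening-onset AE that intensifies on XP-8121 is counted depends on how the site records it

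*SAP*

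**What the plan says.** **Definition and attribution.** SAP 6.9.2: "A TEAE is defined as any adverse event which occurs on or after the first dose of study drug". On study periods the same section says "TEAEs will be attributed to treatment periods by comparing the start date/time of the event to the date/time of first dose" in each period. It does not mention a change in severity of an event already present.

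**Dates.** SAP 8.3 resolves incomplete AE dates conservatively, "if there is any possibility that the available partial information could reasonably result in the AE being treatment-emergent". It acts on missing or partial start and end dates only.

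**What counts as an AE.** Protocol 12.1.1.1 includes "the deterioration of a pre-existing medical condition following or during exposure to a pharmaceutical product". Protocol 12.6 adds that clinically significant abnormal findings "that are present at Screening and worsen after consent are included as AEs".

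**What is recorded.** Protocol 12.3: "Information about AEs will be collected from the signing of consent form and followed until resolution", subject to a follow-up limit. For each AE, "the Investigator will evaluate and report the onset (date and time), resolution (date and time), intensity, causality" and further items. Nothing is said about opening a new record when intensity rises.

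**Where it is used.** SAP 6.6 makes the incidence, frequency, severity and drug relationship of TEAEs part of the primary endpoint. SAP 9.8.2 lists the tables: one row for any AE, with the remaining rows and all the SOC/PT summaries restricted to TEAEs.

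**The concern.** AE collection opens at consent, and Screening can start 28 days before the first dose, so some subjects may reach first dose with an AE already open. If such an event is mild at onset and becomes severe after an up-titration, the clinically relevant part happens on XP-8121. A flag built on the start date alone would not see it.

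The trial makes this pattern plausible. Subjects arrive on oral levothyroxine, and Protocol Appendix B lists non-specific signs of thyroid excess such as palpitations, tiredness and nervousness. Protocol 7.4.2 itself recognises that these begin and worsen at different times and rates. A rule that can miss worsening during titration bears directly on the safety objective, and it can only lower the TEAE count. That is at odds with the SAP's other conventions: missing severity is summarised as severe, missing relationship as related, and incomplete dates lean toward treatment-emergent.

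**Working it through.** No arithmetic applies. The check is to follow each kind of worsening through the two documents and see where it lands.

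**How the flag would be programmed.** SAP 6.9.2 uses the verb occurs, which could mean the start of the record or the time of worsening. The period rule in the same section uses the start date/time, SAP 8.3 imputes start and end dates only, and no date of worsening is defined anywhere in the SAP. The natural reading for a programmer is start date on or after first dose.

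**Cases.**

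| Situation | Governing text | Result under SAP 6.9.2 |
|---|---|---|
| Condition present before consent, deteriorates on XP-8121 | Protocol 12.1.1.1 makes the deterioration an AE | New AE with post-dose onset: counted |
| Clinically significant finding present at Screening, worsens after first dose | Protocol 12.6 makes the worsening an AE | Counted, if dated at the worsening |
| AE opened in Screening, worsens after dosing, site opens a new record | Not required by either document, not forbidden | Counted, in the period of the new start date |
| AE opened in Screening, worsens after dosing, original record kept | Protocol 12.3 has no instruction on this | Pre-dose start: not a TEAE |
| AE with an incomplete start date that could be post-dose | SAP 8.3 | Imputed to be treatment-emergent |

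Only the fourth row fails. The date rule in SAP 8.3 does not rescue it, because its start date is complete and pre-dose.

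**What the fourth row loses.** The event is absent from the TEAE row, from the drug-related row even if judged related, and from the severe row even if it ends as severe. It is also absent from the SOC/PT tables by severity and by relationship. It remains in the any-AE row of the SAP 9.8.2 overall summary and in the listing of all AEs under Protocol 13.7.1.

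**Direction.** The third and fourth rows describe the same clinical event and differ only in data entry. One route adds a TEAE and the other does not. No route adds a TEAE that should not be there, so any error is an undercount.

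**Size.** It would need four quantities: the proportion of subjects with an AE open at first dose, the proportion of those AEs that worsen, the proportion kept on one record, and, for overall incidence, the proportion of affected subjects with no other TEAE. The documents give none of them.

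**The case against.** The strongest counter-argument is that the SAP says occurs, not starts, and that the protocol makes deterioration during exposure an AE in its own right. On that view a worsening on XP-8121 occurs after the first dose and already meets the definition. Protocol 12.3 points the same way for disease-related events, which are recorded when more frequent, severe or prolonged than expected. This stands for any worsening entered as its own event, and it covers symptoms that subjects already had on oral therapy before consent.

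A reader might therefore go too far and infer that every event starting in Screening and worsening on drug is left out of every TEAE table. The documents do not support that: the first three cases in the table above are counted.

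Three further points limit the consequence. The eCRF completion guidelines are not among the documents, and Protocol 17 places data management detail in a separate plan, so a new-record instruction may already exist. Protocol 13.7 tests no safety hypothesis, so no decision rule turns on this. Subjects are counted once, so someone with another TEAE does not change overall incidence, and a rise from mild to moderate would never enter the severe row.

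What remains is the AE already open from Screening and kept on one record. Nothing in either document settles how it is recorded or whether it is treatment-emergent.

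**Conclusion.** The point holds in a limited form. SAP 6.9.2 leaves the treatment-emergent status of one class of event to site recording practice: onset between consent and first dose, still open at first dose, more severe afterwards, and kept on the original record. The conclusion assumes that the flag is programmed on start date, which is the reading that SAP 6.9.2 and 8.3 favour, and that at least some sites do not open a new record.

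The bias, if any, is toward fewer TEAEs in a primary safety endpoint. A reader might want to put it in percentage points of TEAE incidence, but any such figure would rest wholly on guessed rates, so none is given. The effect may be nil if site instructions already require a new record. The gap is nevertheless worth closing, because the definition feeds the main safety tables and the correction is cheap.

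**What to change.** 1. In SAP 6.9.2, define a TEAE as an AE that starts on or after the first dose, or that starts before it and worsens in severity on or after it. Attribute a worsened event to the study period in which the worsening occurred, and tabulate it at its worsened severity.
2. Confirm that the eCRF completion instructions require a post-dose increase in severity to be entered as a new record with its own date, or add that line. Without a date of worsening, the period rule in step 1 cannot be applied. Where a new record exists, only that record should carry the treatment-emergent flag, so that event counts are not doubled.
3. Before database lock, query every AE that was ongoing at first dose for any later increase in severity and its date.

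The cost is one SAP sentence, one eCRF line that may already exist, and one round of queries limited to AEs open at first dose. The downside is that reported TEAE counts, including severe and related ones, may be slightly higher.

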6.9.3 Clinical Laboratory Assessments

Changes from baseline for all hematology and chemistry data will be calculated as: *the visit value minus the baseline value*. Maintenance Period records will also display changes from Titration Period Baseline.

Laboratory results will be classified as Abnormal if outside of the normal range in either direction, as Low if below the lower limit of normal, and as High if above the upper limit of normal.

The investigator will classify relevant laboratory results as clinically significant (CS) in the eCRF.

6.9.4 Electrocardiograms

Changes from baseline for all ECG parameters (heart rate [beats/min], QT interval [ms], PR interval [ms], QRS interval [ms], RR interval [ms], the corrected QT interval using Fridericia's formula [QTcF; ms], and the corrected QT interval using Bazett's formula [QTcB; ms]) will be calculated as: *the visit value minus the baseline value*. Maintenance Period records will also display changes from Titration Period Baseline.

Clinical significance of ECG interpretation will be determined by the investigator and overread by the cardiologist. While both results will be listed, only the overread by the cardiologist will be summarized in tables.

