- d: Following the initial dose and any up-titration, subjects will be required to return for an outpatient visit 72 hr [ $\pm 1$  day] after the up-titration has occurred for the following assessments: ECG, vital signs, abbreviated physical examination, T4 and TSH collections and monitoring of AEs and non-study medications.
- e: See Section 12.8.2 for details on complete and abbreviated physical examinations.

Protocol XP-8121-120

XP-8121 (levothyroxine sodium) injection

- f: **12-lead ECG** to be assessed prior to vital signs and blood draws. ECGs will be taken after remaining in the supine position for at least 10 minutes. Note that at Screening only, the order of ECGs, vital signs, and blood draw procedures are allowed to vary. All potentially clinically significant automated ECG readings should be repeated within 5 minutes of the reading. If potentially clinically significant reading is confirmed, then the ECG will be sent to a local cardiologist for review (Section 12.8.5). See Section 11.5 for further details on procedure order. [Table 3](#) outlines windows for assessment timepoints.
- g: **Vital signs:** triplicate measurements of systolic and diastolic BP and heart rate/pulse will be taken at intervals of 1 to 2 minutes after being in a supine position for at least 10 minutes. Respiratory rate and oral body temperature will also be measured. When the time of scheduled vital sign measurements coincide with a blood draw, vital sign measurements are to be performed before the blood draw where possible, ensuring the blood draw is within the window specified in the protocol. See Section 11.5 for further details on procedure order. [Table 3](#) outlines windows for assessment timepoints.
- h: **Clinical Safety Laboratory evaluation** (hematology, chemistry, and urinalysis): Clinical safety laboratory testing will be performed at Screening, the beginning and the end of the Maintenance Period, and the ET Visit, if needed. Subjects are required to fast from all food and drink except water for  $\geq 10$  hr prior to collection when glucose values will be obtained. Fasting will not be required for the other safety laboratory testing, and when a safety recheck is deemed necessary and the glucose value is not included. See Section 11.5 for further details on procedure order.

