### 12.8.5. Electrocardiogram

12-lead ECGs are to be performed prior to vital signs with subjects in a supine position at least 10 minutes before the reading is taken. See [Table 3](#) for timing window allowances with respect to measurement collection.

All ECG tracings will be reviewed and assessed by the Investigator or designee. All potentially clinically significant automated ECG readings should be repeated within 5 minutes of the reading. If potentially clinically significant reading is confirmed, then the ECG will be sent to a local cardiologist for review.

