6.2.3 Baseline

Two baselines are defined for this study as the last evaluable measurement taken prior to the date/time of the first dose of study drug administration in the Titration Period (prior to any dose of study treatment) and prior to the date/time of the first dose of study drug administration in the Maintenance Period. For electrocardiograms, if a cardiologist interpretation is available on this record, this value will be used as baseline for the appropriate period.

Vital signs (blood pressure, heart rate) baseline will use the average of the triplicate assessments in the last timepoint occurring prior to the first dose of study drug treatment administration for each treatment period.

All change from baseline analyses will use the Titration Period baseline across all records in addition to the Maintenance Period baseline on records only from the Maintenance Period, as applicable.

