9.8.4 Electrocardiograms

Visit values and changes from baseline to each post-baseline visit will be summarized with descriptive statistics (n, mean, SD, median, minimum, and maximum) by treatment period for all ECG parameters:

heart rate (beats/min), QT interval (ms), PR interval (ms), QRS interval (ms), RR interval (ms), QTcF (ms) and QTcB (ms).

Subject counts and percentages for ECG interpretation and clinical significance as reported on the eCRF by the investigator (and confirmed by cardiologist) will be presented for visit results and shifts from baseline to each visit. Cardiologist's overread will take precedence if it differs from investigator's assessment.

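### SAP 6.9.4 tabulates only the cardiologist's reading of ECG clinical significance, but the protocol sends few ECGs to a cardiologist and SAP 9.8.4 and 6.2.3 use a different rule

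*SAP*

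**What the plan says.** **Protocol.** Section 12.8.5 gives every tracing to the site: "All ECG tracings will be reviewed and assessed by the Investigator or designee". A cardiologist sees only a subset: "If potentially clinically significant reading is confirmed, then the ECG will be sent to a local cardiologist for review". Table 2 footnote f repeats this routing and gives the step that comes before referral: "All potentially clinically significant automated ECG readings should be repeated within 5 minutes of the reading".

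**SAP 6.9.4.** This section describes two readings: "Clinical significance of ECG interpretation will be determined by the investigator and overread by the cardiologist". It then says that both will be listed but that "only the overread by the cardiologist will be summarized in tables".

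**SAP 9.8.4.** This section specifies the tables. For the categorical ECG results, shown as counts and percentages, the wording is: "as reported on the eCRF by the investigator (and confirmed by cardiologist) will be presented for visit results and shifts from baseline to each visit". It adds that the cardiologist's "overread will take precedence if it differs from" the investigator's assessment. Heart rate and the QT, PR, QRS, RR, QTcF and QTcB intervals are summarised separately, with no condition about an overread.

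**SAP 6.2.3.** For ECG baseline, "if a cardiologist interpretation is available on this record, this value will be used as baseline".

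**SAP section 5.** The only listed departure from the protocol's analyses concerns dose-normalised PK parameters. Nothing is said about ECG reading.

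**The concern.** The 6.9.4 sentence works only if every ECG has a cardiologist's overread, and the protocol does not arrange for that. An ECG that the investigator reads as normal, with no flagged automated reading, never leaves the site. Under 6.9.4 that ECG contributes nothing to the interpretation table; under 9.8.4 it is counted. For an ECG without an overread a programmer cannot follow both.

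What is at stake is the meaning of the reported percentage. Clinically significant ECGs are named within the primary safety endpoint (Protocol 13.5.1, SAP 6.6). A table confined to overreads describes ECGs that were selected because they looked abnormal. A table of all ECGs describes the treated subjects. Shift tables suffer more, because a shift needs a usable result at baseline as well as at the visit. Clinically significant ECG abnormalities at Screening are an exclusion (criterion 10), so overreads at the Titration Period baseline should be uncommon.

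**Working it through.** The documents give no ECG referral rate and no explicit denominator for these tables, so there is no plan figure to reproduce. The check has two parts.

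**1. What each section does with an ECG**

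| ECG | Protocol 12.8.5 | SAP 6.9.4, literal | SAP 9.8.4 | SAP 6.2.3, if baseline |
|---|---|---|---|---|
| Not flagged, or flagged and not confirmed | Investigator reading only | Not tabulated | Investigator result tabulated | Investigator result stands |
| Flagged and confirmed | Investigator reading plus cardiologist review | Overread tabulated | Overread prevails if the two differ | Cardiologist value used |

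The sections agree on the second row and part on the first, which will hold most ECGs. A rule of precedence on disagreement has a purpose only if the investigator's result is otherwise used. The conditional wording in 6.2.3 likewise accepts that some ECGs have no overread.

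Protocol section 13 lets the SAP override the protocol's statistical methods. That does not settle the matter, because who reads an ECG is a study procedure. The SAP cannot tabulate readings that the protocol never generates.

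**2. Possible size under a literal 6.9.4**

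Inputs:
- N = 44 subjects (Protocol 7.2). This is an upper figure, since visits after up-titration will have fewer.
- p = the share of ECGs referred at a visit. Assumed, ranged from 2% to 20%.
- q = the share of referred ECGs that the cardiologist calls clinically significant. Assumed, 10% to 50%.

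Formulas:
- Overreads per visit = N × p. ECGs without one = N × (1 − p).
- Subjects with an overread at both baseline and visit = N × p² if the two are independent, and N × p at most.
- Probability of no overread at a visit = (1 − p)^N.

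| p | Overreads | No overread | Pairs, independent | Pairs, maximum | P(no overread at visit) |
|---|---|---|---|---|---|
| 2% | 0.9 | 43.1 | 0.02 | 0.9 | 41% |
| 5% | 2.2 | 41.8 | 0.11 | 2.2 | 10% |
| 10% | 4.4 | 39.6 | 0.44 | 4.4 | 1% |
| 20% | 8.8 | 35.2 | 1.8 | 8.8 | about 0% |

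The share called clinically significant is q among overreads (10% to 50%) and p × q among all ECGs (0.02 × 0.10 = 0.2% up to 0.20 × 0.50 = 10%).

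The denominator matters as much as the referral rate. Take assumed counts of 44 ECGs, 3 overread and 1 clinically significant:
- overreads as denominator: 1/3 = 33%;
- all subjects as denominator, with the missing-data category that SAP 8.1 prescribes for categorical summaries: 1/44 = 2.3% clinically significant and 41/44 = 93% missing;
- the 9.8.4 rule: 1/44 = 2.3%, with the other 43 ECGs classified by their available reading.

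**The case against.** The strongest reply is that 9.8.4 is the analysis section and already states a workable rule, supported by 6.2.3. A programmer who follows those two gets full denominators and baselines. The 6.9.4 sentence can also be read in harmony with them: it speaks of both results being listed, so it may mean only that the overread is tabulated where both exist. This stands in part. It shows that the defect is a conflict between sections, not a settled choice to analyse overreads alone. It does not remove the conflict, because 6.9.4 does not say that it applies only where two readings exist, and the parenthesis about cardiologist confirmation in 9.8.4 could itself be taken to require an overread.

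Three stronger readings are tempting, and the documents do not support them:

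- **That the ECG tables as a whole are compromised.** The sentence concerns clinical significance of the interpretation. The seven numeric parameters and their changes from baseline carry no overread condition.
- **That the percentage clinically significant would be inflated to something like 33%.** That needs overreads as the denominator, which no section states. SAP 8.1 points instead towards a missing category.
- **That a safety signal would be hidden.** Both readings are listed, clinically significant ECG findings are listed under SAP 9.5, and those that meet the adverse event definition are recorded as adverse events (Protocol 12.6) and so reach the adverse event summaries.

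Exclusion criterion 10 should not be pressed too far either. It bars significant abnormalities, not ECGs that were flagged, referred and then judged not significant. Baseline overreads may be few, but the documents do not say how few.

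**Conclusion.** The inconsistency is real. SAP 6.9.4 conflicts with SAP 9.8.4 and 6.2.3, and it does not fit the protocol's selective referral. Applied literally, it would leave most ECGs out of the interpretation, clinical-significance and shift-from-baseline tables, or show them as missing: roughly 35 to 43 of 44 at a visit if 2% to 20% are referred. Those rates are assumptions, and whether the loss appears as a smaller denominator or as a missing category is not stated. A reader might infer that wrong denominators and nearly absent baselines are the plan; they follow only if 6.9.4 is preferred to the sections that contradict it.

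Severity is minor to moderate. The tables are descriptive, no hypothesis is tested on safety data (Protocol 13.7), and the individual readings remain available. It still deserves correction, because the tables bear on a primary safety endpoint and two programmers could produce materially different versions of them.

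**What to change.** Replace the last sentence of SAP 6.9.4 with the rule in 9.8.4: list both readings; tabulate the cardiologist's overread where one exists and the investigator's assessment otherwise; take all subjects with an ECG at that visit as the denominator. For shifts, apply the same rule at baseline, as 6.2.3 already implies.

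Reword the parenthesis in 9.8.4 so that cardiologist confirmation applies only to ECGs that were referred. A footnote giving the number of overread ECGs at each visit would show which reader the table rests on.

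If a cardiologist's overread of every ECG was in fact intended, Protocol 12.8.5 and Table 2 footnote f would have to say so, and that would be a change of procedure. Otherwise the cost is a few words in the SAP, with no new data, visits or readings.
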